Group 1. Conversational Voice Assistant Standard Loneliness Routine (CVA-S) Participants in the CVA-S group will receive an a priori set of evidence-based interactions to perform with the conversational voice assistant. The interaction dose will be 15 minutes performed once in the morning and once in the evening, at pre-set times. The participants will 1) do a meditation activity, 2) play an interactive trivia game, and 3) ask the assistant to tell a joke.

Group 2. Conversational Voice Assistant Enhanced Loneliness Routine (CVA-ELR) Participants in the CVA-ELR group will receive personalized intervention activities based on individual preferences and personality. The interaction dose will be 15 minutes performed once in the morning and once in the evening, at pre-set times and as needed. After collection of post-intervention data, participants will be compensated for their time.

Procedures

An appointment will be scheduled to set up Alexa, review instructions, and perform data collection by study personnel (Omaha and Lincoln). The instructions for both groups will include basic training by study personnel (Omaha and Lincoln) on how to use the conversational voice assistant. Then review of the loneliness routine based on group assignment. Data will be collected at pre (baseline) and post intervention (after 12-weeks).

Data

Pain Severity and Pain Interference: Subjective pain will be measured using the Brief Pain Inventory Short form (BPI-SF). The instrument has nine questions that measure pain severity and pain interference with function. The severity questions assess pain numerically ranging from 0 no pain to 10 pain as bad as you can imagine; interference questions assess interference from 0 no interference to 10 completely interferes. Higher scores indicate higher severity or interference with 0 being none, 1-3 mild, 4-6 moderate, 7-10 severe. The BPI-SF has Cronbach alphas ranging from 0.86-0.96.

Loneliness: Subjective social isolation and loneliness will be measured using the University of California Los Angeles, UCLA Loneliness Scale Version 3, a 20-item instrument with responses of never, rarely, sometimes, and always. There is no standard accepted score for identifying loneliness; higher scores reflect greater reported loneliness. The scale has established validity and reliability with Cronbach's alphas ranging from 0.85 to 0.94.

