Depression: Will be measured as it may interfere with pain and loneliness. We will use the Geriatric Depression Scale Short form. The instrument has 15 questions with higher scored indicating depression.

Self-management of Pain: PROMIS Self-Efficacy for Managing Symptoms-SF-8: an eight-item tool that allows the subjects to report the level of confidence to manage/control their symptoms, to manage their symptoms in different settings (home, public place, an unfamiliar place), and to keep their symptoms from interfering with work, sleep, relationships, or recreational activities.

Objective Use: We will securely access the participants voice assistant profiles and document the time stamps of intervention activities to assess frequency and length of use, type of uses, and routine completion rates with the standard and enhanced loneliness routines.

Usability: Usability will be measured using the System Usability Scale. The 10 question 5-point Likert scale scores range from 0-100 and scores above 68 are above average.

Personality Inventory: The Big Five Inventory is a 40-item assessment of general personality using the five-factor model Neuroticism (N), Extraversion (E), Openness to Experience (O), Agreeableness (A), and Conscientiousness (C).

Statistical Analysis

Descriptive statistics to calculate inferential results such as percentages, mean and standard deviations on demographic, health history, BPI-SF, UCLA Loneliness Scale, Geriatric Depression, and PROMIS Self-efficacy scores at baseline and after the 12-week intervention.

We will compare the average questionnaire scores within and between the CVA-S and CVA-E groups. The Shapiro-Wilk test used to assess the normality of distributions for these variables. Given the significant results, indicating non-normal distributions from the Shapiro-Wilk test for these variables except baseline pain severity and post-study severity, Wilcoxon Signed-Rank non-parametric test was chosen for hypothesis testing of all variables except baseline pain severity and post-study severity, which were tested by paired-samples t-test. In addition, ANOVA tests were performed to compare the baseline scores of self-reported pain severity, pain interference, loneliness, depression, and self-efficacy between the CVA-S and the CVA-E groups.

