Mann-Whitney U test was employed to test differences between the standard and enhanced conditions in terms of routine initiation rates and SUS scores. Multiple regression analyses were conducted to explore the relationships between participants' SUS scores, objective use of the routines with personality.

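### Does the between-arm test on an undefined routine initiation rate, with no stated test of completion or length of use, call for a change to the plan?

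*Combined protocol and SAP*

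**What the plan says.** **Planned measures.** Under Data, the Objective Use paragraph states: "We will securely access the participants voice assistant profiles and document the time stamps of intervention activities". The purpose is to "assess frequency and length of use, type of uses, and routine completion rates with the standard and enhanced loneliness routines".

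**Stated analyses of use.** The Statistical Analysis section has one between-arm analysis of device use: "Mann-Whitney U test was employed to test differences between the standard and enhanced conditions in terms of routine initiation rates and SUS scores". It gives no numerator, denominator or time window. The same section relates objective use to personality by multiple regression and states no arm contrast there. The general within- and between-group comparison covers questionnaire scores, and the ANOVA covers baseline questionnaire scores. The sentence on descriptive statistics does not list use data.

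**What each arm is asked to do.** For the standard arm, Study Groups says: "The interaction dose will be 15 minutes performed once in the morning and once in the evening, at pre-set times". Its activities are fixed: "do a meditation activity, 2) play an interactive trivia game, and 3) ask the assistant to tell a joke". The enhanced arm has the same 15-minute dose with personalised activities, performed "once in the morning and once in the evening, at pre-set times and as needed".

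**Training.** Under Procedures: "The instructions for both groups will include basic training by study personnel (Omaha and Lincoln) on how to use the conversational voice assistant", followed by "Then review of the loneliness routine based on group assignment".

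**The concern.** There are two grounds for unease.

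1. **The tested quantity is not one of the planned ones.** Frequency, length, type and completion are to be recorded. Initiation is tested. Starting a routine does not show that 15 minutes were delivered, so equal initiation could in principle sit alongside unequal exposure.

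2. **The counting rule bears on the feature that differs by arm.** Only the enhanced arm is told it may use the routine on demand. If unscheduled starts are counted, the test compares use under the assigned intervention. If they are not, it compares adherence to a common schedule. Both questions are legitimate, but they differ, and the text does not say which was asked.

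At stake is the reading of the only stated between-arm comparison of engagement. The comparisons of pain, loneliness, depression and self-efficacy do not depend on it.

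**Working it through.** The documents give no figure for use, sample size or adherence, so there is nothing to reproduce. The check sets the planned measures against the stated analyses, then gauges how far the counting rule could matter.

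**Step 1: coverage.**

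| Planned measure (Data, Objective Use) | Named in a between-arm test? |
|---|---|
| Frequency of use | No; initiation rate is the nearest match |
| Length of use | No |
| Type of use | No |
| Routine completion rate | No |

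The description of the gap is accurate. However, the Data section says these measures will be assessed, which plans measurement in both arms. It does not promise a hypothesis test for each one.

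**Step 2: denominator.** From the documents: two sessions (morning and evening), 15 minutes each, 12 weeks. Assumed: every day of the week, which is implied but not stated.

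- Scheduled sessions: 2 × 7 × 12 = 168 per participant.
- Scheduled time: 168 × 15 = 2,520 minutes.
- On a five-day week: 2 × 5 × 12 = 120 sessions.

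**Step 3: effect of the counting rule with behaviour held fixed.** Let p be scheduled adherence, equal in both arms, with one unscheduled start a week (12 in total) in the enhanced arm only. Both inputs are assumptions. The standard arm's rate is p.

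| Rule for the enhanced arm | Formula | p = 40% | p = 60% | p = 80% |
|---|---|---|---|---|
| Pre-set starts only | 168p/168 | 40% | 60% | 80% |
| All starts, unscheduled starts also in the denominator | (168p + 12)/180 | 44.0% | 62.7% | 81.3% |
| All starts over scheduled sessions | (168p + 12)/168 | 47.1% | 67.1% | 87.1% |

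The largest shift is 12/168 = 7.1 points per net unscheduled start per week (enhanced minus standard). It is 3.6 points at a net 0.5 a week, 14.3 at a net 2, and 0 if unscheduled use is equal in the two arms. On the five-day reading it is 12/120 = 10.0 points per net start.

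If unscheduled sessions replaced scheduled ones and only pre-set starts counted, the enhanced rate at p = 60% would be (100.8 − 12)/168 = 52.9%. That is a change in behaviour, since scheduled adherence would then differ between the arms. It does not belong in the range due to the counting rule.

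**Step 4: effect on the test.** The Mann-Whitney test uses ranks. With equal follow-up for everyone, dividing each participant's starts by 168, by 120 or by 12 weeks leaves the ranks, and so the test, unchanged. A missing fixed denominator therefore does not affect the test. What remains open is whether unscheduled starts enter the count. The percentage-point figures in Step 3 apply only if the rate is taken over scheduled sessions, and they do not translate into a rejection rate.

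**Step 5: starts versus delivered dose.** At 60% initiation, scheduled minutes delivered are 0.60 × 2,520 × s, where s is the share of each session completed: 378 minutes at s = 25% and 1,512 at s = 100%. This is a wide range for one participant, but nothing in the documents suggests that s differs by arm, so it does not describe an arm difference.

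**The case for a change.** The best case for acting is that the text leaves the one stated engagement comparison open to two readings, in a design where the instruction on unscheduled use differs by arm. Neither the questionnaire comparison, the ANOVA, the descriptive sentence nor the regressions fills the gap. The logs exist, and a few sentences would define the rate and add between-arm comparisons of completed sessions and total minutes.

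Part of this stands. The term is undefined, and a reader of the results needs to know the denominator and whether unscheduled starts were counted.

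The rest does not carry the argument as far as a change of plan:

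- Testing one use measure in a pilot and describing the others is a fair choice. Two further tests would be a matter of preference.
- The passage on this test is written in the past tense, so added comparisons would be post hoc. They would also need a completion rule, chosen after the fact, that works for both fixed and personalised activities, and that brings discretion of its own.
- It is not certain that the added comparisons would need no new data. The plan logs time stamps of intervention activities and does not establish that standard-arm use outside the assigned routine is captured.
- Unscheduled use in the standard arm is not forbidden, and both arms are trained on the device, so even the sign of the net difference in unscheduled use is unknown.

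**Conclusion.** The observation is accurate but does not call for a change. This is missing detail that an analyst fills sensibly, for instance by taking starts over pre-set sessions, and the Mann-Whitney test is sound under that or any other sensible definition. The planned measures of completion and length can be tabulated by arm within the plan as written.

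No wrong or biased result has been shown. Under the assumptions of a daily schedule, 60% scheduled adherence in both arms and one unscheduled start a week in the enhanced arm only, the counting rule moves the enhanced rate by at most 7.1 points, from 60% to 67.1%. With equal unscheduled use in both arms the arm difference is 0. Adherence and unscheduled use are not given in the documents. What is left is ordinary care in reporting: say how initiation was counted, and present any comparison of completion or minutes as descriptive or exploratory. The pain and loneliness results are unaffected.

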The Loneliness Epidemic Tailoring Interventions to Reduce Loneliness and Pain

NCT05387447

08-21-2023

Protocol

Setting and Recruitment

We will recruit participants: 1) direct referral from those with ethical access in independent or assisted and independent living facilities and 2) community and social media marketing. A copy of a letter of support will be uploaded from each senior retirement apartment. We will host informational sessions (PI, Co-Is, and study personnel) with question-and-answer periods at the facilities (in Omaha and Lincoln) to inform participants about the study. We will obtain permission from these facilities prior to placing flyers at any locations in the community and hosting study informational presentations. Interested individuals will undergo screening and enrollment.

The sites where the study will be conducted are the *participant's place of residence at the following locations*: Aksarben Village Senior Apartments Trinity Courtyard Senior Apartments (both in Omaha, NE) Eastmont Senior Living Apartments and The Legacy Senior Living (all in Lincoln, NE).

Screening

Study personnel (Omaha and Lincoln) will screen interested potential subjects according to inclusion and exclusion criteria in the private residence. Those meeting eligibility will undergo informed consent.

Inclusion: 1) men and women 60 years of age; 2) live alone (single-family home, independent, or assisted living); 3) self-report have experienced or currently experiencing musculoskeletal pain; and 4) wireless internet access via a broadband Internet connection.

Exclusion: 1) memory loss as evidenced by poor performance on the Mini Cog; 2) inability to speak English; 3) prior study participation; 4) prior use or current use of a conversational voice assistant; and 5) not willing to engage with the voice assistant.

Both UNMC and UNL personnel will conduct screening, enrollment, Alexa set-up with instructions and training, data collection, data analysis and interpretation.

Enrollment and Randomization

Once all participants are recruited and enrolled, participants will be randomly assigned with equal distribution to the conversational voice assistant-standard group (CVA-S) or the conversational voice assistant-enhanced loneliness routine treatment group (CVA-E). The study will be a 12-week randomized pilot trial.

Study Groups

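### Do the exploratory personality regressions need a named term for randomised arm?

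*Combined protocol and SAP*

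**What the plan says.** The only description of these models is the last sentence of the Statistical Analysis section. It says that multiple regressions were run to explore how personality relates to "SUS scores, objective use of the routines with personality". Outcomes, predictors and covariates are not listed.

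Other sections bear on the point:

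- **Enrollment and Randomization:** "participants will be randomly assigned with equal distribution" to the two groups, so allocation is 1:1. The study is called a pilot and no sample size is given.
- **Study Groups:** the standard group "will receive an a priori set of evidence-based interactions to perform with the conversational voice assistant", whereas the enhanced group "will receive personalized intervention activities based on individual preferences and personality". The enhanced group's sessions take place "at pre-set times and as needed"; the standard group has only the pre-set times.
- **Data, Objective Use:** the device logs are used to assess "frequency and length of use, type of uses, and routine completion rates with the standard and enhanced loneliness routines".
- **Statistical Analysis, the sentence before the regressions:** a Mann-Whitney test addresses "differences between the standard and enhanced conditions in terms of routine initiation rates and SUS scores".

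**The concern.** The plan treats an arm difference in usability and routine use as possible, because it tests for one. The next sentence then relates the same variables to personality without mentioning arm. If the arms do differ, a model with personality alone leaves that difference in the residual and widens the intervals for the trait slopes. Arm is known for every participant, so adjusting for it seems free.

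There is also a question of meaning. Personality helps to define the treatment in one arm and not in the other. A single pooled slope is then an average over a fixed routine and a tailored one, and a reader could take it for something more general. These regressions are the only stated analysis linking personality to use or usability.

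**Working it through.** The documents give no sample size, standard deviation, arm difference or significance level, so there is no planned figure to reproduce. The check asks what an arm term would do over a range of assumptions.

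**Inputs from the documents:** 1:1 randomisation; five personality traits (Data, Personality Inventory).

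**Assumptions:** all five traits enter together and are independent and normal; usability and use are the outcomes; intervals are two-sided 95%; the outcome has within-arm SD 1; one trait has slope 0.5 in absolute size, so the residual variance is 1 - 0.5² = 0.75; the arms differ by *d* SD; total sample size is *N*.

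**Step 1. Effect on the residual.** Under 1:1 allocation, leaving arm out adds about d²/4 to the residual variance. At d = 0.5 this is 0.0625 on 0.75, or 8%. At d = 1.0 it is 0.25 on 0.75, or 33%.

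**Step 2. Cost of the term.** Residual degrees of freedom fall from N - 6 to N - 7. The squared cost factor is

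r = [(N - 7)/(N - 8)] × [t(N - 7)/t(N - 6)]²,

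where t is the 97.5% point. At N = 40: (33/32) × (2.0345/2.0322)² = 1.034.

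**Step 3. Ratio of interval widths, with arm to without arm.**

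ratio = √{ r / [1 + (d²/(4 × 0.75)) × N/(N - 1)] }.

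At N = 40 and d = 0.5: √(1.0336/1.0855) = 0.976. The ratio equals 1 at d = 2 × √[0.75 × (r - 1)(N - 1)/N].

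| Total N | r | d = 0 | d = 0.5 | d = 1.0 | break-even d |
|---|---|---|---|---|---|
| 12 | 1.380 | +17.5% | +12.5% | +0.6% | 1.02 |
| 16 | 1.160 | +7.7% | +3.2% | -7.5% | 0.67 |
| 20 | 1.099 | +4.8% | +0.5% | -9.8% | 0.53 |
| 30 | 1.050 | +2.5% | -1.7% | -11.6% | 0.38 |
| 40 | 1.034 | +1.7% | -2.4% | -12.2% | 0.31 |
| 50 | 1.025 | +1.2% | -2.8% | -12.5% | 0.27 |
| 80 | 1.014 | +0.7% | -3.3% | -12.9% | 0.21 |

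Simulation agrees closely from N = 20 upwards. At N = 40 it gives ratios of 1.016, 0.976 and 0.877 for d = 0, 0.5 and 1.0. At the smallest sizes the formula slightly overstates the cost: with d = 0, simulation gives +14% at N = 12 and +7% at N = 16.

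**Step 4. In absolute terms.** At d = 0.5 the simulated interval for the slope goes from 0.63 to 0.61 wide with 20 per arm, and from 0.55 to 0.53 with 25 per arm. In 30-40% of single trials the interval comes out wider with arm than without.

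**Step 5. Bias.** The mean slope is the same with and without arm, to 0.001. In a single trial, chance imbalance moves it with SD 0.04-0.05 at d = 0.5. The half-width at 20 per arm is 0.63/2 = 0.315, so the movement is about a sixth of it or less.

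**Step 6. Slopes that differ by arm.** A main-effect arm term does not capture these. When the slope is -0.5 in one arm and 0 in the other, the model estimates about -0.25 with or without arm. Estimating the contrast needs trait-by-arm terms, and its interval is about 1.26 wide at 20 per arm and 1.09 at 25, so it would say little about a true difference of 0.5.

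**The case for a change.** The best case for a change is that the documents themselves make arm relevant: tailoring on personality and as-needed use occur in one group only, and the plan tests both variables for arm differences. The trade also looks lopsided. At 20 to 25 per arm the worst average outcome is an interval 1-2% wider and the best considered is about 12% narrower. One sentence would settle the matter, and without it the regressions cannot be reproduced from the text.

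Part of this stands. The sentence is incomplete, and a pooled slope does average over two routines. Including arm is a reasonable choice with about 30 or more participants in total and an arm difference above roughly 0.3-0.4 SD.

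It does not establish a fault. The 12% needs an arm difference of a full SD, for which the documents offer no support. The favourable trade depends on a sample size that they do not state, and it reverses in a very small pilot. The strongest part of the argument, tailoring on personality, points to slopes that differ by arm, and the arm term leaves that untouched. Finally, a simple statement that arm was included would answer the concern in full, which marks it as a matter of reporting.

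**Conclusion.** No change to the plan. The text is a one-sentence summary of exploratory models that is silent on every model term, arm included. An analyst writing up these regressions will have to list outcomes and predictors, and whether arm was among them will be visible then. The documents already organise use and usability by condition, so nothing suggests that arm was overlooked.

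The likely effect on the results is small: a 2-3% average narrowing at 0.5 SD with 20 to 25 per arm, a 1-2% widening if there is no difference, and no change in the expected slope. The arm comparisons of usability and initiation rates rest on the Mann-Whitney tests and are unaffected.

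This rests on assumptions. Sample size and arm difference are not in the documents. The absence of bias requires that personality was measured before assignment or is unaffected by it, and the timing of the inventory is not stated. It also takes usability and use both as outcomes. The sentence could be read as relating usability to use and personality jointly; use arises after randomisation, so the figures above would not cover that model. The percentages come from normal outcomes and may not carry over exactly to a bounded usability score.
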